6.2 Toxicity Management

The management of specific AEs (including AE of special interest of rash) and laboratory parameters is described in the Operations Manual. Specific management for elevated hepatic function tests is described in this protocol in Section 5.5.

7 STATISTICAL METHODS & DETERMINATION OF SAMPLE SIZE

7.1 Statistical and Analytical Plans

Complete and specific details of the statistical analysis will be described and fully documented in the Statistical Analysis Plan (SAP). The SAP will be finalized prior to the interim database lock. The statistical analyses will be performed using SAS (SAS Institute Inc., Cary, North Carolina, USA).

7.2 Definition for Analysis Populations

The full analysis set (FAS) includes all randomized subjects who received at least 1 dose of study drug. The FAS will be used for all efficacy and baseline analyses. Subjects will be grouped according to treatment as randomized.

The safety analysis set consists of all subjects who received at least 1 dose of study drug. For the safety analysis set, subjects are assigned to a treatment group based on the treatment actually received, regardless of the treatment randomized.

7.3 Statistical Analyses for Efficacy

All efficacy analyses will be conducted on the FAS based on treatment as randomized.

For the primary efficacy endpoint in both Part 1 and Part 2, the null hypothesis that the within-group absolute change from baseline in ppFEV₁ through Day 29 is zero will be tested for each treated group at 2-sided alpha of 0.05. The primary analysis will be performed using a mixed-effect model with repeated measures (MMRM) with change from Baseline in ppFEV₁ as the dependent variable; treatment group, visit, and treatment-by-visit interaction as fixed effects; subject as a random effect; and baseline ppFEV₁ as a covariate. The estimate for the within-group mean change along with the 95% confidence intervals and the corresponding *P* values will be calculated as the primary analysis. The treatment effect compared to placebo will be estimated using the same model.

The secondary endpoints of sweat chloride, ppFEV₁, FVC, and FEF₂₅₋₇₅ will be analyzed based on an MMRM model similarly as the primary endpoint.

Details on the efficacy analyses are provided in the SAP.

Sample Size Estimation

The power calculations are provided for the most potentially efficacious groups with the combination treatment for both Part 1 and Part 2 for the primary efficacy endpoint. Placebo groups from both Part 1 and Part 2 will be combined in the Part 2 efficacy analysis. A sample size of 18 subjects in a group will provide 80% power to detect a 5.3% absolute increase from baseline in ppFEV₁ for that group assuming a standard deviation of 7.5%. When comparing to the placebo group, a sample size of 18 subjects in both treated group and placebo group will provide 80% power (Part 1), or a sample size of 18 subjects in treated group and 27 subjects in placebo group will provide approximately 87% power (Part 2), to detect a 7.3% effect size in ppFEV₁ change from Baseline assuming the standard deviation of 7.5% for change in ppFEV₁ for both groups.

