4.2 Discussion of Study Design

Choice of Control Group

The control group consists of subjects randomly assigned to receive placebo.

The ABBV-3067 single-agent treatment groups (i.e., Regimens A and B) also serve as control groups for the dual combination treatment groups, in order to demonstrate the contribution of ABBV-2222.

Although there are dual combination products that have been approved to treat CF subjects who are homozygous for the F508del mutation, these products are not yet considered standard of care in all countries where this study will be conducted. In countries where dual combination products are accessible as standard of care, this design will also allow the participation of CF subjects who are not on dual combination products due to concerns about safety or tolerability, lack of efficacy, or other concerns (see Eligibility Criteria #21).

Appropriateness of Measurements

Standard statistical, clinical, and laboratory procedures will be utilized in this study. All efficacy measurements in this study are standard for assessing disease activity in subjects with CF. All clinical and laboratory procedures in this study are standard and generally accepted.

Suitability of Subject Population

This study was designed to enroll subjects with a confirmed clinical diagnosis of CF who are also homozygous for the F508del CFTR mutation because ABBV-2222 and ABBV-3067 are CFTR modulators designed to restore the expression and function of F508del CFTR. This population is the most likely to demonstrate a significant change in sweat chloride and ppFEV₁ when given a combination of ABBV-2222 and ABBV-3067.

Selection of Doses in the Study

Part 1

ABBV-2222 has been evaluated following multiple doses in healthy volunteers (Study GLPG2222-CL-101) and patients with CF who are homozygous for F508del mutation in a Phase 2 study (Study GLPG2222-CL-202), at dosages ranging from 50 mg QD to 600 mg QD. ABBV-2222 was safe and well tolerated at all dosages tested. In Study GLPG2222-CL-202, patients with CF who were dosed with ABBV-2222 for 29 days, there was a trend of dose-dependent decrease in SwCl was observed between 50 mg and 200 mg doses on Day 15 and Day 29, with maximum decrease in SwCl observed in the 200 mg dose group.

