## **2.4 Sample Size Determination**

The power calculations are provided for the most potentially efficacious groups with the combination treatment for both Part 1 and Part 2 for the primary efficacy endpoint. Placebo groups from both Part 1 and Part 2 will be combined in the Part 2 efficacy analysis. A sample size of 18 subjects in a group will provide 80% power to detect a 5.3% absolute increase from Baseline in ppFEV1 for that group assuming a standard deviation of 7.5%. When comparing to the placebo group, a sample size of 18 subjects in both treated group and placebo group will provide 80% power (Part 1), or a sample size of 18 subjects in treated group and 27 subjects in placebo group will provide approximately 87% power (Part 2), to detect a 7.3% difference in ppFEV1 change from Baseline between a treated group and the placebo group assuming the standard deviation of 7.5% for change in ppFEV1 for both groups.

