## **8.0 Efficacy Analyses**

### **8.1 General Considerations**

All efficacy analyses will be conducted for the FAS. All tests will be 2-sided at an alpha level of 0.05. For each part of the study, the efficacy analysis will be performed after all ongoing subjects have completed the study part and the database has been locked.

For the primary efficacy endpoint, the null hypothesis that the within-group absolute change from baseline in ppFEV1 through Day 29 is zero will be tested for each treated group at 2-sided alpha of 0.05.

Unless otherwise specified, any subject who is randomized based on a wrong stratum will be analyzed according to the actual stratum to which the subject belongs.

"Baseline" refers to the last non-missing observation before the first administration of study drug.

Unless otherwise specified, continuous variables will be analyzed using Mixed-Effect Model Repeat Measurement (MMRM) method with the model based mean and standard error being provided. The Baseline and visit means will also be presented for each treatment group among subjects who have both Baseline and at least one post Baseline visit values. Treatment groups will be compared using MMRM model as described in Section 8.2. Point estimates and 95% CIs of mean change from Baseline within each treatment group, the difference between each active treatment group and placebo, and the difference between each combination therapy arm and the ABBV-3067 150 mg monotherapy arm (Part 1 only) will be provided. Note that both placebo arms in Part 1 and Part 2 will be combined into one placebo group for the Part 2 model comparison.

Plots of the primary endpoint and certain secondary endpoints by treatment group will be used to visualize the change of endpoint values over time and the difference between treatment groups.

Use of bronchodilator medications and/or airway clearance techniques may affect lung function measurements in the short term. Therefore, post-baseline spirometric measurement that are collected inconsistently with the conditions for the baseline spirometric measurement will be excluded from the efficacy analysis. For example, if baseline spirometric measurement was collected prior to bronchodilator use, then any spirometric measurement collected post bronchodilator use at a subsequent visit will be excluded from analysis.

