## **8.3 Primary Efficacy Endpoint(s) and Analyses**

### **8.3.1 Primary Efficacy Endpoint(s)**

The primary endpoint is the absolute change from Baseline through Day 29 in ppFEV1. The predicted values of FEV1 (L) at all study visits will be estimated for age, gender, and height using the 2012 Global Lungs Initiative equation. Percent predicted FEV1 is the ratio of FEV1 (L) to the predicted FEV1 (L), expressed as a percentage. For the primary efficacy endpoint in both Part 1 and Part 2, the corresponding statistical null hypotheses are that there is no difference in the mean value of ppFEV1 from baseline through Day 29 within each treatment group.

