### **8.3.3 Primary Efficacy Analysis**

The primary analysis will be performed using MMRM with change from Baseline in ppFEV1 as the dependent variable. The mixed model includes the categorical fixed effects of treatment, visit and treatment-by-visit interaction, as well as the continuous fixed effect of baseline ppFEV1. The random effects of the model will be subject ID. Parameter estimation will use the method of restrictive maximum likelihood (REML).

The point estimate for the primary endpoint from the MMRM model along with the 95% confidence interval and the corresponding p-value will be presented for the primary efficacy analysis. The pairwise comparison of the primary endpoint of ppFEV1 between each active treatment group versus the placebo group will also be estimated using the same model. The Least Squares Mean of the treatment difference between each active treatment group versus the placebo group will be presented along with the 95% confidence interval and a 2-sided p-value.

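### The primary test asks whether each treated arm's ppFEV1 change differs from zero, not whether it differs from the randomised placebo arm that the plan already compares and powers.

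*Protocol*

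**What the plan says.** Protocol 4.2 is plain about the comparator: "The control group consists of subjects randomly assigned to receive placebo". It adds that the ABBV-3067 single-agent arms serve as further controls for the combination arms.

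The primary hypothesis does not use that control. Protocol 7.3 says "the null hypothesis that the within-group absolute change from baseline in ppFEV₁ through Day 29 is zero will be tested for each treated group", at two-sided 0.05, and on the within-group mean, its interval and its P value continues: "values will be calculated as the primary analysis. The treatment effect compared to placebo will be estimated using the same model". The SAP agrees. Section 8.1 has the change "through Day 29 is zero will be tested for each treated group at 2-sided alpha of 0.05", and section 8.3.1 frames the null as no difference "from baseline through Day 29 within each treatment group".

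The placebo comparison is in the plan, in second place. SAP 8.3.3, the section on the primary efficacy analysis, says the pairwise comparison "between each active treatment group versus the placebo group will also be estimated using the same model", and that the least squares mean difference "will be presented along with the 95% confidence interval and a 2-sided p-value".

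Both results are powered in protocol 7.3 and SAP 2.4. The first statement is within group: "A sample size of 18 subjects in a group will provide 80% power to detect a 5.3% absolute increase from Baseline", with an SD of 7.5. The second is against placebo at 7.3 points with the same SD: 80% for 18 v 18 in Part 1, and approximately 87% for 18 v 27 in Part 2, where the placebo arms of both parts are pooled.

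**The concern.** A mean change from baseline contains everything that moves ppFEV1 over four weeks, whatever the treatment. A randomised placebo arm is there to estimate that part so that it can be subtracted. Testing each treated arm against zero leaves it in.

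One possible source of shared change is in the protocol itself. Section 5.4 asks that the first dose be timed close to the first day of an inhaled-antibiotic cycle. For subjects on on/off cycles, baseline could then fall at the end of an off period and later spirometry on antibiotic, in every arm. This is an inference: the documents give neither its size nor the number of such subjects.

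At stake is what the report presents as the primary result. An arm with no advantage over placebo could be correctly labelled positive under the plan. Where the within-group and placebo results disagree on the same data, the plan gives precedence to the one that ignores the control.

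**Working it through.** **Inputs.** SD of change 7.5 points in every group, two-sided alpha 0.05, within-group effect 5.3, placebo-difference effect 7.3 (protocol 7.3, SAP 2.4). Arm sizes are from protocol 4.1: 9 in A, B, C, I and M (M is placebo), and 18 in the others, including placebo arm H. Pooled placebo in Part 2 is 18 + 9 = 27. Simple t-tests (noncentral t for power) are used; they ignore the MMRM's baseline covariate and repeated visits and assume that every subject contributes.

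**Step 1: reproduce the stated powers.** The noncentrality is d / (7.5/√n) within group and d / (7.5·√(1/n₁ + 1/n₂)) against placebo.

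| Test | Effect | Recomputed | Stated |
|---|---|---|---|
| Within group, n=18 (17 df) | 5.3 | 80.7% | 80% |
| 18 v 18 (34 df) | 7.3 | 81.0% | 80% |
| 18 v 27 (43 df) | 7.3 | 87.8% | about 87% |

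All three reproduce. The normal approximation gives 85.0%, 83.1% and 89.2%, so the plan evidently used t-tests.

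**Step 2: what each test needs to see.**
- Within group, n=18: 2.110 × 7.5/√18 = 2.110 × 1.768 = 3.73 points.
- 18 v 18: 2.032 × 7.5 × √(2/18) = 2.032 × 2.5 = 5.08 points.

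If the treated and placebo arms both rise by 3.73, the primary test is significant, yet the difference is 0 with 95% CI −5.1 to +5.1.

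**Step 3: one data set, two answers.** Take an observed rise of 4.5 in a treated arm of 18 and a placebo change of 0.
- Within group: t = 4.5/1.768 = 2.55 on 17 df, p=0.021.
- Against placebo: t = 4.5/2.5 = 1.80 on 34 df, p=0.081.

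**Step 4: an inert arm under a shared rise.** The documents give no placebo change, so the rise is an assumption shown over a range. Entries are the chance of a significant improvement (upper tail).

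| Shared rise (points) | Within group, n=18 | Within group, n=9 | Against concurrent placebo |
|---|---|---|---|
| 0 | 2.5% | 2.5% | 2.5% |
| 1 | 7.7% | 5.4% | 2.5% |
| 2 | 18.6% | 10.5% | 2.5% |
| 3 | 36.0% | 18.4% | 2.5% |

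**Step 5: Part 2 pooling.** If a rise s occurred in Part 2 only, the pooled placebo mean would move by s × 9/27, leaving a bias of s × 18/27 in the contrast. For s = 1, 2 and 3 the bias is 0.67, 1.33 and 2.00 points. With a standard error of 7.5 × √(1/18 + 1/27) = 2.28, an inert 18-subject arm is significantly better about 5%, 8% and 14% of the time. The pooled contrast removes part of such drift, not all of it.

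**Step 6: power if the contrast becomes primary.**

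| Active arm | Effect | Within group | Part 1 contrast | Part 2 pooled contrast |
|---|---|---|---|---|
| n=18 | 5.3 | 81% | 54% (18 v 18) | 62% (18 v 27) |
| n=18 | 7.3 | 97% | 81% | 88% |
| n=9 | 7.3 | 73% | 63% (9 v 18) | 69% (9 v 27) |

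The effect detectable at 80% power for an 18-subject arm is 5.26 within group, 7.21 for 18 v 18 and 6.54 for 18 v 27. The concurrent-only Part 2 contrast, 18 v 9, has 63% power at 7.3 points.

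**The case against.** The strongest reply is that the controlled result is already there. Any reader of the report will see the placebo difference, its interval and its p-value, and in Part 1 the difference from ABBV-3067 150 mg as well (SAP 8.1). This is a dose-ranging study with no multiplicity procedure and no early efficacy stop (SAP 12.0). Dose selection rests on safety, tolerability, efficacy and pharmacokinetics together, and the protocol's interim section is redacted, so no decision can be shown to turn on the primary test. All of that stands, and it is why this is an inexpensive improvement rather than a serious flaw.

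The numbers also have limits. With no shared drift, the within-group test keeps its 2.5% upper tail; a placebo arm of 18 would then rise by 3.73 or more only about 1.7% of the time. The gap between 3.7 and 5.1 points reflects the larger standard error of a two-sample contrast, not bias. The 8% to 36% figures rest on assumed rises. The plan also limits drift through stable regimens, consistent bronchodilator timing and exclusion of inconsistent spirometry. These safeguards may make drift smaller, but they do not estimate what remains, whereas the placebo arm does.

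Finally, the hypotheses in protocol 2.1 are improvement from baseline and superiority over monotherapy; superiority over placebo is not among them. But protocol 4.2 names placebo first and describes the monotherapy arms as additional controls for showing the contribution of ABBV-2222. Placebo is also the only comparator that serves every active arm and the only one for which the plan gives power.

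**Conclusion.** The concern holds. The plan randomises a placebo control, estimates and powers the difference from it, and then gives primary status to a test that does not use it. Followed as written, it can report a positive primary result for an arm no better than placebo.

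That the test ignores the control is plain from the text and needs no assumption. The thresholds of 3.7 and 5.1 points rest on the plan's own SD and arm sizes and on simple t-tests. The inflated rates for an inert arm depend on a shared rise that the documents do not quantify. The consequence is confined to which result is labelled primary, since the placebo contrast will be reported in any case.

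**What to change.** - In protocol 7.3 and SAP 8.1, 8.3.1 and 8.3.3, state the primary null for each active arm as no difference from placebo in mean ppFEV1 change through Day 29, tested with the MMRM contrast already specified. Report within-group means with 95% CIs as descriptive.
- In protocol 7.3 and SAP 2.4, make the 7.3-point calculation the primary power statement and label the 5.3-point figure as within-group only.
- Align the hypothesis in protocol 2.1 that speaks of improvement from baseline.
- For Part 2, state that 18 of the 27 pooled placebo subjects are non-concurrent, so a difference in drift between the parts is not fully removed. Add the contrast against the 9 concurrent placebo subjects as a supportive sensitivity analysis; at about 63% power for 7.3 points it cannot be more than that.

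No new subjects, visits or data are needed. The protocol changes require an amendment with ethics review (protocol 8.1). The statistical price is the loss of nominal power shown in step 6 of the working. The plan claims power only for the 18-subject groups, and at 7.3 points those keep 81% in Part 1 and 88% in Part 2.

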7.4 Statistical Analyses for Safety

All safety analyses will be performed on the safety analysis set for both Part 1 and Part 2 based on the treatment subjects actually receive. Safety will be assessed by AEs, AESIs, weight, vital signs, clinical laboratory data, 12-lead ECGs, pulse oximetry and spirometry. Details on the safety analyses are provided in the SAP.

AEs will be coded using Medical Dictionary for Regulatory Activities (MedDRA). A treatment-emergent adverse event (TEAE) is defined as an AE with an onset date on or after the first dose of study drug and within 30 days after the last dose of study drug. The number and percentage of subjects experiencing TEAEs will be tabulated using MedDRA system organ class (SOC) and preferred term (PT), as well as by severity and by relationship to the study drug as assessed by the investigator. Summaries (i.e., number and percentages) of TEAEs, SAEs, deaths, AEs leading to discontinuation, and AESIs will be provided.

For laboratory test and vital signs variables, mean change from baseline and percentage of subjects with evaluations meeting criteria for predefined potentially clinically significant (PCS) values will be summarized.

7.5 Pharmacokinetic and Exposure-Response Analyses

Individual ABBV-2222 and ABBV-3067 plasma concentrations at each study visit will be tabulated and summarized with appropriate statistical methods.

Data from this study may be combined with data from other studies for the population pharmacokinetic and exposure-response analyses. Population pharmacokinetic and exposure-response analyses of data only from this study may not be conducted. The following general methodology will be used for the population pharmacokinetic and exposure-response analyses.

[REDACTED]

Additional analyses will be performed if useful and appropriate.

7.6 Interim Analysis

[REDACTED]

8 ETHICS

8.1 Independent Ethics Committee/Institutional Review Board (IEC/IRB)

The protocol, informed consent form(s), recruitment materials, and all subject materials will be submitted to the IEC/IRB for review and approval. Approval of both the protocol and the informed consent form(s) must be obtained before any subject is enrolled. Any amendment to the protocol will require review and approval by the IEC/IRB before the changes are implemented to the study. In addition, all changes to the consent form(s) will be IEC/IRB approved.

8.2 Ethical Conduct of the Study

The study will be conducted in accordance with the protocol, Operations Manual, International Council for Harmonisation (ICH) guidelines, applicable regulations, and guidelines governing clinical study conduct and the ethical principles that have their origin in the Declaration of Helsinki. Responsibilities of the investigator are specified in [Appendix B](#).

8.3 Subject Confidentiality

To protect subjects' confidentiality, all subjects and their associated samples will be assigned numerical study identifiers or "codes." No identifiable information will be provided to AbbVie.

9 SOURCE DOCUMENTS AND CASE REPORT FORM COMPLETION

The investigator is responsible for ensuring the accuracy, completeness, legibility, and timeliness of the data reported. All source documents should be attributable, legible, contemporaneous, original, accurate, and complete to ensure accurate interpretation of data. Clinical site monitoring is conducted to ensure that the rights and well-being of human subjects are protected, that the reported trial data are accurate, complete, and verifiable, and that the conduct of the trial is in compliance with the currently approved protocol, ICH Good Clinical Practice (GCP), and applicable federal, state, provincial, country-specific, and local laws and regulatory requirement(s).

10 DATA QUALITY ASSURANCE

AbbVie will ensure that the clinical trial is conducted with a quality management system that will define quality tolerance limits in order to ensure human subject protection and reliability of study results. Data will be generated, documented, and reported in compliance with the protocol, ICH GCP, and applicable federal, state, provincial, country-specific, and local laws and regulatory requirements.

11 COMPLETION OF THE STUDY

The end of study is defined as the date of the last subject's last visit.

APPENDIX A. STUDY SPECIFIC ABBREVIATIONS AND TERMS

Abbreviation	Definition
ABPA	Allergic bronchopulmonary aspergillosis
AE	Adverse event
AESI	Adverse events of special interest
ALT	Alanine aminotransferase
AST	Aspartate aminotransferase
ATS	American Thoracic Society
BID	Twice daily
cAMP	Cyclic adenosine monophosphate
CF	Cystic fibrosis
CFTR	CF transmembrane conductance regulator
CL/F	Oral clearance
C _{max}	maximum observed concentration
CRO	Clinical research organization
CTCAE	Common Terminology Criteria for Adverse Events
CYP	Cytochrome P-450
DMC	Data monitoring committee
EC ₅₀	Effective concentration providing 50% of the maximal response
EC ₉₀	Effective concentration providing 90% of the maximal response
ECG	Electrocardiogram
ERS	European Respiratory Society
EudraCT	European Clinical Trials Database
FAS	Full analysis set
FEF ₂₅₋₇₅	Forced expiratory flow at mid-lung capacity
FSH	Follicle-stimulating hormone
FVC	Forced vital capacity
GCP	Good Clinical Practice
GLI	Global Lung Function Initiative
HBE	Human bronchial epithelial/epithelium
HBsAg	Hepatitis B virus surface antigen
HCV	Hepatitis C virus
HIV	Human immunodeficiency virus

ICF	Informed consent form
ICH	International Council for Harmonisation
IEC	Independent ethics committee
IMP	Investigational medicinal product
IMPD	Investigational Medicinal Product Dossier
IRB	Institutional review board
IRT	Interactive response technology
IU	International Unit
IUD	Intrauterine device
IUS	Intrauterine hormone-releasing system
MedDRA	Medical Dictionary for Regulatory Activities
MMRM	Mixed-effect model with repeated measures
N/A	Not applicable
PCS	Potentially clinically significant
PD	Pharmacodynamics
ppFEV ₁	Percent predicted forced expiratory volume in 1 second
PT	Preferred term
QD	Once daily
QTc	QT interval corrected for heart rate
QTcF	QT interval corrected for heart rate using Fridericia's formula
SAE	Serious adverse event
SAP	Statistical analysis plan
SOC	System organ class
SUSAR	Suspected unexpected serious adverse reactions
SwCl	Sweat chloride
TBD	To be determined
TEAE	Treatment-emergent adverse event
ULN	Upper limit of normal
V/F	Volume of distribution

